6 INTERVENTION ARM

6.1 *Intervention Arm*

Randomized PLWD-CG dyads are offered:

- A telephone orientation visit with a study coach to acquaint the caregiver to the 6-session STAR-VTF program and online learning environment.
- A paper-based and electronic manual to identify priority behaviors, develop plans for addressing behaviors, and make plans for pleasant events.
- 6 weekly telephone coaching visits lasting 30 minutes and corresponding to each of the 6 training modules.
- Secure message (email) support within the patient portal, as needed, with the coach to help with personalizing the STAR-VTF curriculum for up to 6 months, as initiated by the caregiver.

We anticipate that self-directed caregiver training with support from social workers will enhance caregivers' sense of competence and self-efficacy. Training caregivers on good communication and the ABCs of dementia problem-solving will lead to decreased activation of behavioral triggers, lower incidence of problem behaviors, and lower caregiver stress in response to behaviors. Assisting caregivers to engage in higher levels of pleasant activities will enhance PLWD and caregiver mood and create a more positive care environment. With increased insight into the natural disease history, caregivers will be able to reframe behaviors as symptoms of dementia rather than insensitivity, rudeness, or deliberate provocation. We hypothesize that changes in the physical and psychosocial environment that reduce triggering events and improve caregiver-PLWD dyadic interactions will reduce the need for and use of antipsychotic medication.

6.2 *Eligibility Confirmation*

Once a PLWD is identified using the automated algorithm, a REDCap database is populated with the potential participants once per week. There are three steps to confirming eligibility.

- A study staff person will review the PLWD medical record to confirm that the person has a diagnosis of ADRD, an emergency contact or other family/friend is listed in the record, and that the PLWD does not live in an adult family home, skilled nursing facility, or memory facility.
- If eligible after medical record review, the staff person will contact a study coach (clinician) who will send a staff message within the EHR to the physician who prescribed the antipsychotic medication to the PLWD. The prescribing clinician will be asked:
 - Is [PLWD] capable of making health care decisions for themselves? [YES/NO/SOMETIMES]
 - Do you believe [PLWD] will live at least 6 months from today? [YES/NO]

- Was [antipsychotic medication] prescribed for behavioral/psychological symptoms of dementia? [YES/NO]
- Is there any other reason to NOT invite this patient and family caregiver to be in the research study? [YES/NO]

Recruitment will not proceed without a response to these questions by the prescribing clinician.

In the third stage, a study staff person will mail an invitation letter to the PLWD-CG dyad. This is followed by a screening phone call approximately 3 business days later. The purpose of the screening call is to determine:

- Willingness to take part in the study regardless of the randomization group.
- Ability to read and speak English.
- Determine whether the CG has ever been diagnosed with Alzheimer's disease or related dementia
- Confirm the PLWD does not live in an adult family home, assisted living facility, skilled nursing facility, or memory facility.
- Whether the caregiver is 21 years or older.
- Whether the caregiver lives in the same household as the PLWD or within 8 miles (30 minutes).
- Whether the caregiver spends at least 8 hours providing care to the PLWD
- Whether the caregiver is the DPOA and if not who that person is.
- Whether the caregiver is the spouse or adult child of the PLWD
- Caregiver access to a computer or other device where the caregiver can access the patient portal, personal email and websites to complete the online training.
- Whether the caregiver uses MyChart – the Kaiser Permanente patient portal - to email the doctors that care for the PLWD
- Administer the Short Portable Mental Status Questionnaire to the caregiver.

If the PLWD-CG dyad remains eligible after the 3-step verification process then a study staff person will randomize the dyad in REDCap and schedule an orientation telephone visit.

If the caregiver is not the DPOA and the PLWD is unable to consent, the study staff person will request the contact information of the person who is DPOA. If the dyad is otherwise eligible, the DPOA will be contacted to obtain verbal consent on behalf of the PLWD.

6.3 *Consent*

6.3.1 *Verbal Consent for screening questions*

Following the recruitment packet mailing, two things may happen:

1. Potential participants may call our study line and express interest in participating or decline to participate. Those expressing an interest will receive a phone call from a Research Specialist and those who decline to participate will be coded as such and not contacted.
2. If we have not heard from the potential caregiver participant, we will follow-up with a phone call to assess interest and eligibility.

During the screening phone call, the Research Specialist will describe the study, answer any questions, and administer a phone screening questionnaire to assess eligibility after verbal consent is given.

6.3.2 *Verbal Consent for participation in study*

If the PLWD-CG dyad is eligible after the phone screening questionnaire, an orientation phone visit will be scheduled. A study coach will obtain verbal informed consent from the caregiver on the day of their orientation phone visit prior to any study activities. The coach will read the consent forms to the caregiver and PLWD, emphasizing that study participation is voluntary and that if the caregiver or PLWD decides not to participate, the decision will have no impact on the care of the PLWD. The coach will also explain that the caregiver or PLWD can stop the consent process or the study at any point if they decide they no longer want to participate. The caregiver and PLWD will have an opportunity to ask questions prior to giving verbal consent. The caregiver and PLWD will have a copy of the consent forms mailed to them with the invite letter and will be instructed to have these in front of them during the call.

6.3.3 *Caregiver is not the DPOA or Priority Person*

If the caregiver is not the DPOA or priority person, and either the doctor or the caregiver have indicated that they believe the PLWD is unable to consent for themselves, we will contact the DPOA or priority person to obtain verbal consent for the PLWD to participate in the study prior to scheduling the orientation phone visit. A study staff member will contact the DPOA/LAR, describe the study in detail, and answer any questions. The study staff member will get verbal consent from the DPOA or legally authorized representative (LAR) for the PLWD to participate. The study staff member will mail a copy of the consent form to the DPOA/LAR following the phone call. If the DPOA/LAR gives verbal consent for the PLWD to participate, study staff will then call the caregiver to schedule the orientation phone visit. The purpose of this is to avoid scheduling a phone visit and randomizing a dyad should the DPOA not give consent for the PLWD to participate.

The consent process will vary depending on the following factors:

- (1) The PLWD is able to consent for themselves. The PLWD's provider will inform the study coach as to his/her medical opinion to the PLWD's incompetence (the provider's response to this question is required in order for the PLWD and caregiver to participate).
- (2) The PLWD is not able to consent for themselves and the caregiver IS either the DPOA or the priority person authorized to make decisions on the PLWD's behalf.
- (3) The PLWD is not able to consent for themselves and the caregiver is **not** the DPOA or the priority person authorized to make decisions on the PLWD's behalf.

Under Case #1, the PLWD gives consent on their own behalf. Under case #2, the caregiver gives verbal consent on behalf of the PLWD. If possible, we will get verbal assent from the PLWD as well. Under case #3, prior to the visit study staff will speak with the DPOA or the priority person authorized to make decisions on behalf of the PLWD and get verbal consent for the PLWD to participate in the study. A copy of the consent form will be mailed to the DPOA or priority person for their records.

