5 STUDY ENROLLMENT AND WITHDRAWAL

5.1 *Inclusion and Exclusion Criteria for Persons Living with Dementia*

The investigators will identify and recruit PLWD-CG dyads in which the PLWD has filled a new prescription for an antipsychotic medication. The study programmer will identify potential PLWD-CG dyads using an automated data algorithm that queries claims data and electronic health record (EHR) data on a weekly basis.

Because we will enroll dyads, there are inclusion/exclusion criteria for both persons living with dementia and their caregivers.

Persons with dementia inclusion criteria:

- Aged \geq 65 years
- Diagnosis of Alzheimer's Disease or related dementia (ADRD)
- Expected to live \geq 6 months from enrollment

Persons with dementia exclusion criteria:

- A diagnosis of bipolar disorder or schizopreniform disorder
- The primary care physician's opinion is that the person with dementia is expected to live less than 6 months.
- Primary language is not English (patient requires a translator).

5.2 *Inclusion and Exclusion Criteria for Caregiver Subjects*

Potentially eligible caregivers are identified by the family contact information in the electronic medical record.

Caregiver inclusion criteria:

- Aged \geq 21 years
- Lives with person with dementia or within 8 miles
- Provides at least 8 hours of care per week

Caregiver exclusion criteria:

- Diagnosis of Alzheimer's Disease or related disorders.
- Caregiver is not the spouse or adult child of the person living with dementia
- Primary language is not English (caregiver requires a translator).

5.3 ***Randomization Assignment Procedures***

5.3.1 ***Randomization Procedures***

The study biostatistician will create a randomization schedule and this will be uploaded into a REDCap database. Caregivers who remain eligible for the study after screening will be randomized within REDCap following the pre-set randomization schedule. All eligible caregiver-patient dyads will be block randomized to ensure comparable numbers of dyads enrolled in each study arm. Caregivers will be categorized according to age (<75 years, >=75 years), sex, and spouse/non-spouse.

R, an open-source statistical computing software, will be used to generate an even number of control and intervention assignments within each block.

5.3.2 ***Blinding***

Study staff will be blinded to study arm when verifying subject eligibility.

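### Dyads are randomized before the caregiver's study consent and before the baseline survey, so consent is arm-aware and the SAP's baseline score is measured after assignment

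*Protocol*

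**What the plan says.** Three places in the protocol fix when randomization happens. Section 5.3.1: "Caregivers who remain eligible for the study after screening will be randomized within REDCap following the pre-set randomization schedule". Section 6.2, after the three eligibility steps: "then a study staff person will randomize the dyad in REDCap and schedule an orientation telephone visit". Section 6.1 introduces the intervention package, whose first item is the orientation visit, with "Randomized PLWD-CG dyads are offered".

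Consent comes later. Section 6.3.2: "A study coach will obtain verbal informed consent from the caregiver on the day of their orientation phone visit prior to any study activities". Section 5.3.2 states that coaches know the group assignment.

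Section 6.4 puts three things on the orientation call: consent, introduction to the online baseline survey, and a check that the caregiver already has the printed items for the assigned arm. For the intervention arm, the printed item named in section 6.1 is "A paper-based and electronic manual to identify priority behaviors, develop plans for addressing behaviors, and make plans for pleasant events". Section 6.4.1 adds orientation to the learning modules on the same call.

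Two safeguards come before randomization. The screening call in section 6.2 asks about "Willingness to take part in the study regardless of the randomization group". Section 6.3.3 covers the case where the PLWD cannot consent and the caregiver is neither DPOA nor priority person. Staff then contact that person "to obtain verbal consent for the PLWD to participate in the study prior to scheduling the orientation phone visit", and the reason is given: "The purpose of this is to avoid scheduling a phone visit and randomizing a dyad should the DPOA not give consent".

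For the analysis, the SAP (Predictors of interest) adjusts every model for the baseline score. Protocol 7.2.6 describes its covariates, including DSRS and FAQ, as pre-randomization.

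**The concern.** The burden outcome is self-reported by caregivers who know what they have been given. A baseline score taken before assignment cannot be affected by it. A score taken after assignment can be, and adjusting for it then carries part of any shift into the treatment estimate. If reported burden falls at baseline in the STAR-VTF arm, benefit is hidden; if it rises, benefit is inflated.

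Consent has a similar weakness. A caregiver who already holds one arm's materials, and is speaking to a coach who knows the arm, may agree or refuse for reasons linked to the arm. Dyads lost at that step have been randomized but have no survey data.

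The protocol recognizes the hazard in section 6.3.3, but guards against it only where someone other than the caregiver must consent. The caregiver's own consent, a PLWD consenting for themselves, and a caregiver consenting as DPOA or priority person all come after randomization.

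**Working it through.** **Order of events.** Screening call (6.2) → randomization and scheduling (5.3.1, 6.2) → orientation call with consent, survey introduction and materials check (6.3.2, 6.4). The materials check confirms the order independently: arm-specific items can be in hand on that call only if the arm was assigned earlier. The pre-randomization label in 7.2.6 therefore does not fit any covariate taken from that survey. The documents do not say when DSRS and FAQ are collected.

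**Sample size base (7.1).** With d = 0.65, two-sided alpha 0.05 and 80% power, a two-sample t-test needs 38.14, so 39 per arm, as stated. Inflation gives 39 × 1.30 = 50.7, against the stated 50. After 10% loss, 50 × 0.90 = 45 per arm.

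**Assumptions not in the documents.** Standardized scores, no true effect, baseline-to-follow-up correlation r = 0.5–0.6, and a baseline shift s = 0.1–0.3 SD in one arm.

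**Standard error of the baseline-adjusted effect.** √(2/45) × √(1 − r²) = 0.211 × 0.866 = 0.183 at r = 0.5, and 0.211 × 0.8 = 0.169 at r = 0.6.

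**Case A, shift at baseline only.** Size of bias = r × s. **Case B, the same reporting shift at baseline and follow-up.** Size of bias = s − r × s = (1 − r) × s.

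| s (SD) | Case A bias (SD) | Case A bias / SE | Case A type I error | Case B bias (SD) |
|---|---|---|---|---|
| 0.1 | 0.05–0.06 | 0.27–0.36 | 0.059–0.065 | 0.04–0.05 |
| 0.2 | 0.10–0.12 | 0.55–0.71 | 0.085–0.110 | 0.08–0.10 |
| 0.3 | 0.15–0.18 | 0.82–1.07 | 0.130–0.187 | 0.12–0.15 |

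A simulation of 6,000 trials with 45 per arm gives Case A biases of 0.048–0.061, 0.101–0.119 and 0.152–0.177, in agreement. A shift of 0.3 SD would be 0.3/0.65 = 46% of the planned effect before any module or coaching call, so the low end is more plausible.

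**Differential refusal.** Assume 10% refuse in one arm and 5% in the other, with refusal correlated ρ = 0.2–0.5 with burden or prognosis. Bias = ρ × k × [φ(z₁₀)/0.90 − φ(z₀₅)/0.95], where z₁₀ and z₀₅ are the normal cut-offs for refusal of 10% and 5%. The bracket is 0.195 − 0.109 = 0.086. The factor k runs from r = 0.5 (selection through baseline, no adjustment) to √(1 − r²) = 0.866 (selection on other prognosis). Results: 0.009–0.015 SD at ρ = 0.2 and 0.022–0.037 SD at ρ = 0.5.

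**The case against.** The strongest reply concerns size. The shift, the correlation and the refusal rates are all assumed, and the direction is unknown. Willingness to join either arm is screened first, consent forms go out with the invitation, and if the survey is submitted promptly, exposure before it is limited to knowing the arm and holding printed materials. Detailed procedures sit in a Manual of Procedures that is not among the documents. All of this stands, and it is why the low end is preferred.

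Three stronger readings are tempting, and the documents do not support them.

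- Because section 3.1 calls the outcome a change, a reader might infer that the whole shift passes into the result. That needs a change score without baseline adjustment. The SAP adjusts for the baseline score, and regressing change on arm and baseline gives the same arm estimate as regressing follow-up on arm and baseline.
- A reader might infer that dropping the baseline score cures the problem. It does so only in Case A. If the reporting shift persists, a follow-up-only comparison carries all of it.
- A reader might infer that reordering removes reporting bias altogether. It does not. Caregivers still know their arm at 8 weeks and 6 months. With a clean baseline, a reporting shift at follow-up enters in full (s − r × 0 = s). That is a limit of unblinded self-report, and a contaminated baseline is not a sound correction for it.

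It can also be said that intention to treat, stated in sections 3 and 7.2.1, already covers dyads that never consent. In principle it keeps them. It does not say how dyads without consent or survey data are handled, but that gap alone would be only missing detail.

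**Conclusion.** The order is clear from the text: assignment comes before the caregiver's consent and before the baseline survey, and the person taking consent knows the arm. Harm is possible but not demonstrated. Under the assumptions above, the SAP's adjusted effect could be off by 0.05–0.18 SD if only baseline answers move (type I error 0.06–0.19), or by 0.04–0.15 SD if the same shift persists, with the low end more plausible in either case. Differential refusal adds about 0.01–0.04 SD. These figures do not show that the trial's result would be invalid. The case for change is that a standard reordering, which extends the reasoning already given in section 6.3.3, settles both matters at the source.

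**What to change.** Reorder sections 6.2–6.4:

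1. Keep the early DPOA/LAR consent in section 6.3.3.
2. On the orientation call, record the caregiver's consent and, where it applies, the PLWD's own consent or that of a caregiver acting as DPOA or priority person.
3. Have the caregiver submit the baseline survey, including DSRS and FAQ if collected there.
4. Only then let REDCap release the assignment; arm-specific materials and orientation follow.

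Report the baseline response rate (section 3.2, item 5) among consented dyads, since it would be 100% by construction among those randomized. Reconcile the pre-randomization label in section 7.2.6 with sections 6.2 and 6.4.

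For dyads already randomized under the current order, report pre-consent losses by arm. Show the SAP analysis with and without the post-assignment baseline score as a sensitivity check, and present neither version as free of bias. Without the baseline score, standard errors are larger by a factor of 1/√(1 − r²) = 1.15–1.25.

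Costs: an IRB-approved amendment and a REDCap gate; a possible second contact or short delay before materials arrive; and a randomized sample limited to baseline-survey completers, which narrows a pragmatic trial. If an assumed 5–10% consent but do not submit the survey, randomizing 100 dyads needs 100/0.95 = 106 to 100/0.90 = 112 consents, rounded up.

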6.4 Orientation Call

The purpose of the orientation telephone call is to:

- Make introductions
- Review consent forms and obtain informed consent
- Orient the caregiver to the baseline measures survey site (online) and confirm their ability to login and complete the baseline measure survey
- Confirm the caregiver has received the printed materials corresponding to their study arm

6.4.1 Intervention Arm only

Participants randomized to the intervention arm will also be oriented to the online learning modules. A study coach will give caregivers an overview of the program and assist the caregiver to:

- Navigate to the Kaiser Permanente School learning modules site
- Login using their credentials
- Give an overview of the learning modules, the cadence of completion (one per week), and required homework
- Schedule the first 30-minute check-in regarding Session One of the program.

6.5 Online Learning Modules

There are 6 self-directed learning modules for intervention arm participants to complete. Modules consist of text, figures and audio describing the principles of the STAR Caregivers program. The modules are:

- (1) Introduction to STAR-Caregivers, Overview of Dementia, Principles of Communication
- (2) ABCs of Problem Solving
- (3) Review of ABCs and Modifying Plans
- (4) Pleasant Events
- (5) Review of Pleasant Events, ABCs, Practical Communication
- (6) Pleasant Events for Caregivers

Each module takes between 30 and 45 minutes to complete and participants are expected to complete one module per week. Participants complete the homework and reading assignments following completion of each module. Study coaches review problem solving plans, pleasant events schedules and any questions about the material or individual needs during follow-up phone calls.

6.6 Weekly Coach Phone Calls

Caregivers are invited to participate in weekly, 30-minute phone calls with a study coach to review material from the relevant training session. Coaches will provide ad hoc advice on the nature and disease process of ADRD, realistic expectations for PLWD behavior, practical communication, how to complete/revise ABC problem solving plans, how to complete/revise the pleasant events schedule, and how to obtain formal and informal respite from caregiving.

6.7 Secure Messaging (Email in the patient portal)

Caregivers will be invited to communicate with their coach via email at the completion of the 6-week training program and up to the end of the 6-month follow-up period. Coaches will only respond to messages initiated by caregivers. Telephone support will be given only as necessary.

6.8 Procedures for Training Study Coaches and Fidelity Monitoring

Drs. [name] and [name] are clinical psychologists and the original developers of the STAR Caregivers training program. They will train study coaches on the STAR Caregivers curriculum and consultation best practices.

Drs. [name] and [name] will meet by regular conference call with study coaches to discuss fidelity to the STAR Caregivers program by anonymously discussing case examples.

The study coaches will keep weekly progress notes that include a checklist confirming what content areas are covered from the protocol during the telephone sessions, information about the types of ABC and pleasant event plans developed by caregivers, and the frequency and content of secure messages initiated. Therapist quality control will be assured through a sample of in-person observed sessions overseen by Drs. [name] and [name].

7 STATISTICAL CONSIDERATIONS

7.1 *Sample Size Considerations*

We anticipate enrolling 100 PLWD-CG dyads in the trial (50 per arm), with up to 90 remaining enrolled at 6 months of follow-up (i.e., 10% lost to follow-up).

7.1.1 Statistical Power for Primary Outcome.

We calculated effect sizes for the impact of STAR-C on the Subjective Caregiver Burden scale ($d=0.77$) and the Revised Memory and Behavior Problem Checklist ($d=0.68$) based on the p-values reported for t-tests comparing the STAR-C mean with the routine medical care group mean in prior research. We will power on the RMBPC (primary outcome) and assume a loss of effect size due to the lower intensity of the intervention. Assuming an effect size of 0.65, type-I error of 0.05, power of 80%, and equal sample sizes, we will require 39 dyads in the STAR-VTF arm and 39 dyads in the control arm ($n=78$). We additionally assume it will be necessary to adjust for baseline covariate imbalance and sample attrition, thus, we will inflate our recruitment targets by 30% as we have done in the past. The final recruitment target will be 50 PLWD-CG dyads in each arm.

7.2 *Analysis Plan*

Data will be collected from project tracking systems, the Epic EMR, and other health system data systems for analysis. Baseline, 8 week, and 6 month measures will be collected via an online survey using REDCap functionality.

Data validation and quality assurance checks will be undertaken to ensure data collection during the study is sufficiently reliable.

